## 6.5 Vital Signs Measurements

Vital signs including pulse rate (beats/min), blood pressure (mm Hg), respiration rate (breaths per minute), and temperature (°C), will be summarized as descriptive statistics for baseline value and change from study baseline by BOTOX treatment group for each BOTOX treatment cycle.

Vital sign values will be considered potentially clinically significant (PCS) if they meet both the observed-value criteria and the change-from-baseline criteria. PCS criteria are specified on Table 5. The number and percentage of patients with PCS postbaseline values will be tabulated for each cycle by treatment group. The percentages will be calculated relative to the number of patients with available non-PCS study baseline values and at least 1 postbaseline assessment in the cycle of interest. The numerator will be the total number of patients with available non-PCS study baseline values and at least 1 PCS postbaseline value in the cycle of interest. A supportive listing of patients with PCS postbaseline values will be provided, including the patient number, baseline and all postbaseline (including non-PCS) values.

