### 1.1 Primary Study Objectives and Design

The primary objective is to evaluate the safety and efficacy for the treatment of urinary incontinence due to OAB in patients 12 to 17 years of age who have not been adequately managed with anticholinergic therapy.

Patients may participate in the study for 96 weeks following entry into the study and should have at least 12 weeks follow-up since the last treatment prior to exiting the study. Eligible patients are randomized to 1 of 3 treatment groups in a 1:1:1 ratio:

- 25 units (U) BOTOX (not to exceed 6 U/kg)
- 50 U BOTOX (not to exceed 6 U/kg)
- 100 U BOTOX (not to exceed 6 U/kg)

In order to ensure that an upper dosing limit of 6 U/kg is not exceeded, the actual dose administered will be adjusted based on the patient's weight if necessary.

Patients will be centrally randomized. In order to ensure balance across treatment groups, patients will be stratified by baseline daytime urinary urgency incontinence episodes (a total of  $\leq 6$  episodes or  $> 6$  episodes over the 2-day diary collection period).

Multiple treatments may be administered in this study. Doses received at subsequent retreatments will be determined by the investigator and based on the patient's response to the preceding blinded treatment. The investigator can elect to keep the dose the same or increase the dose compared with the preceding treatment. If it is deemed that a decrease in dose is warranted, the patient will be exited from the study. The first treatment will be administered on day 1.

All patients will be evaluated at scheduled clinic visits at weeks 2, 6, and 12 post-treatment, and thereafter at alternating telephone and clinic visits every 6 weeks until the patient qualifies for further retreatment or exits the study. Patients can request retreatment from week 12 since the preceding treatment. Once qualified for retreatment, the same visit schedule will be followed.

The primary efficacy measure is daytime urinary incontinence episodes, and the primary time point is week 12 after treatment 1.

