#### **3.3 Study Duration**

Patients will participate in the study for at least 96 weeks following entry into the study and should have at least 12 weeks follow-up since the last treatment prior to exiting the study. The minimum duration is therefore 96 weeks, and the maximum duration is approximately 108 weeks (for patients who received their last treatment at week 96 with 12 weeks posttreatment follow-up). Thus, patients could receive a maximum of 8 BOTOX treatment cycles. For details on how to analyze duration of exposure to study treatment see Section [6.1.1](#).

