## 6. Safety Analyses

All analyses will be performed on the BOTOX-treated population. Adverse events and all other safety analyses will be presented by BOTOX treatment cycle in this population and grouped according to the actual dose received at that treatment cycle (25, 50, or 100 U of BOTOX as well as an 'All BOTOX' group).

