## **6.2 Adverse Events**

AEs will be coded from the verbatim text into preferred term and the primary SOC by using the MedDRA dictionary. Events will be summarized by BOTOX treatment cycle.

A treatment-emergent adverse event (TEAE) for the study treatment period is an AE with onset after the initiation of study treatment or an AE with onset prior to study treatment that worsened in severity or became serious after the initiation of study treatment.

For a given treatment cycle, a TEAE is an AE with onset after the initiation of cycle treatment or an AE with onset prior to cycle treatment that worsened in severity or became serious after the initiation of cycle treatment.

An AE that stops during treatment cycle 1 and recurs in treatment cycle 2 is considered as a TEAE in treatment cycle 2 if it fulfills the TEAE definition above with respect to initiation of cycle 2 treatment.

The incidence of TEAEs will be summarized and presented for all events and will be tabulated by treatment group as follows:

- i. By relationship to treatment. Classified for all TEAEs and treatment-related TEAEs.
- ii. By descending order of frequency.
- iii. By primary SOC and preferred term. At each level of summarization (overall, primary SOC, and preferred term) a patient will be counted once if he/she reports 1 or more experiences at that level.
- iv. By primary SOC, preferred term and severity. For a given adverse event of a patient, if more than 1 severity grade was reported, the worst severity grade will be included in the tabulation. Statistical hypothesis tests will not be performed for this summary.

All treatment-related TEAEs (study drug-related, and injection procedure-related adverse events) will be presented. In addition, study drug-related and injection procedure-related AEs will be presented separately.

Treatment-related TEAEs will be analyzed by the same procedure outlined above (ii, iii, and iv). In addition, the number and percent of patients discontinued due to treatment-related TEAEs will also be tabulated by treatment group.

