### 6.4 Clinical Laboratory Evaluations

The clinical laboratory data (hematology, blood chemistry, and urinalysis) will be summarized by BOTOX treatment group for each BOTOX treatment cycle. Descriptive statistics will be generated for baseline values and change from study baseline by visit. Study baseline is defined as the last assessment prior to treatment 1.

Clinical laboratory test values will be considered potentially clinically significant (PCS) if they meet either the lower-limit or higher-limit PCS criteria. PCS criteria are specified on [Table 4](#). The number and percentage of patients who have PCS postbaseline clinical laboratory values will be tabulated for each cycle by treatment group. The percentages will be calculated relative to the number of patients with available non-PCS study baseline values and at least 1 postbaseline assessment during the treatment cycle of interest. The numerator will be the total number of patients with available non-PCS baseline values and at least 1 PCS postbaseline value during the treatment cycle of interest. A supportive listing of patients with PCS postbaseline values will be provided, including the patient number, baseline and all postbaseline (including non-PCS) values.

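### By-cycle PCS tables do not separate new from carried-over abnormalities, so persistent ones are recounted under the later cycle's dose

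*SAP*

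**What the plan says.** SAP 6.5 gives PCS vital signs for each cycle by treatment group. The numerator is the number of "patients with available non-PCS study baseline values and at least 1 PCS postbaseline value in the cycle of interest". The denominator is the number of patients with available "non-PCS study baseline values and at least 1 postbaseline assessment in the cycle of interest". SAP 6.4 treats laboratory values in the same way: a non-PCS baseline and "at least 1 PCS postbaseline value during the treatment cycle of interest". On the reference value, SAP 6.4 says: "Study baseline is defined as the last assessment prior to treatment 1". It is not reset at a retreatment.

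The dose label is set in SAP 6, where safety data are "grouped according to the actual dose received at that treatment cycle". On how dose may change, SAP 1.1 says: "The investigator can elect to keep the dose the same or increase the dose compared with the preceding treatment". A patient for whom a lower dose is thought warranted leaves the study. On the number of cycles, SAP 3.3 says: "Thus, patients could receive a maximum of 8 BOTOX treatment cycles".

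Adverse events follow a different rule. SAP 6.2 says: "For a given treatment cycle, a TEAE is an AE with onset after the initiation of cycle treatment". It also admits an earlier event that worsened in severity or became serious after that cycle's treatment.

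Table 5 of the SAP sets a two-part criterion (observed value and change from baseline) for blood pressure and pulse. Weight has only the change part, 5% in either direction. Laboratory limits in Table 4 are mostly multiples of the laboratory's normal limits, so for them the study baseline acts only as an eligibility filter.

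**The concern.** A patient who first becomes PCS in cycle 1 and stays so, unchanged, meets the numerator again in cycle 2, cycle 3 and so on, although nothing new followed those injections. The same unchanged finding would not be a treatment-emergent event of cycle 2 under SAP 6.2. If the dose was raised in between, the carried-over case appears under the higher dose.

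Safety of repeated treatment is a stated objective (Protocol 2.1), and the by-cycle PCS tables are one of the places where a reader will look for it. A rate that is higher in later cycles or at higher doses could be read as cumulative or dose-related harm when part of it is earlier abnormality still present. Later columns may also be small, since recruitment was stopped early (SAP 15). In an assumed column of 10 patients, one carried-over case adds 10 percentage points.

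**Working it through.** **No figure to reproduce.** The documents state no PCS incidence and no persistence. All rates below rest on assumptions.

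**Recount under persistence.** Let q be the risk of a new PCS value in a cycle and r the fraction of PCS patients who are still PCS in the next cycle, with retreatment unrelated to PCS status. Under the SAP rule the printed rate is p(1) = q and p(c) = r·p(c−1) + [1 − r·p(c−1)]·q. For q = 5% and r = 0.5, cycle 2 gives 0.5 × 0.05 + (1 − 0.025) × 0.05 = 7.4%. For r = 1 the formula reduces to 1 − (1 − q)^c, and 1 − 0.95^8 = 33.7%.

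Printed rate (%) at q = 5%:

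| r | Cycle 1 | Cycle 2 | Cycle 4 | Cycle 8 |
|---|---|---|---|---|
| 0 | 5.0 | 5.0 | 5.0 | 5.0 |
| 0.25 | 5.0 | 6.2 | 6.5 | 6.6 |
| 0.5 | 5.0 | 7.4 | 9.0 | 9.5 |
| 0.8 | 5.0 | 8.8 | 13.9 | 18.5 |
| 1 | 5.0 | 9.8 | 18.5 | 33.7 |

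As r goes from 0 to 1, the cycle 8 rate runs from 2.0% to 14.9% at q = 2%, and from 10.0% to 57.0% at q = 10%.

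If carried-over patients are removed from numerator and denominator, the rate is [1 − r·p(c−1)]·q / [1 − r·p(c−1)] = q in every cycle, whatever r is.

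**Conditions that flatten or reverse the rise.**
- Selective retreatment: if 80% of non-PCS but only 20% of PCS patients are retreated, q = 5% and r = 0.8 give 5.0%, 6.0%, 6.2%, 6.2% and 6.2% over five cycles.
- Shorter later cycles: with 1% transient onset per visit and 6, 4, 3 and 3 visits per cycle, 1 − 0.99^v gives 5.9%, 3.9%, 3.0% and 3.0%.
- Stable values: simulated systolic pressure with no drug effect (mean 113, between-patient SD 8, visit SD 7, four visits per cycle) gives about 1.0% in each of four cycles.

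**Weight.** Assume no drug effect, mean gain of 4% per year, between-patient SD of 3% per year, measurement SD of 1%, and one weight at the end of each 26-week cycle. At t years the change from study baseline has mean 4t and SD √[(3t)² + 1]. At t = 0.5 the mean is 2 and the SD 1.80, so the 5% limit lies 1.66 SD above the mean. Simulated rates over four cycles are 4.8%, 37.9%, 59.5% and 70.5%. With zero mean gain they are 0.6%, 11.4%, 27.8% and 41.1%.

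Judged from the weight before each injection, the 4% case gives 4.8%, 7.3%, 7.3% and 7.3%. The step after cycle 1 arises because this illustration puts measurement error on the reference weight only from cycle 2.

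**Which samples exist.** Protocol 6.3.14 restricts the week 12 sample to the blood count, BUN and creatinine. The other 14 of the 16 chemistry analytes in SAP Table 4 are scheduled only before each injection and at exit. In a non-final cycle their only scheduled value after the injection is the draw before the next one, and SAP Table 2 has no place for that draw other than Day 1 of the next cycle.

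**The case against.** A reader might infer that PCS rates must climb with cycle number by construction. The documents do not support that. The numerator needs a PCS value observed in the cycle itself, and the denominator is rebuilt each time. A resolved abnormality drops out, so a rise needs persistence or drift. Nor is a patient escalated through all three doses counted three times in one comparison: the tables are by cycle, so that patient sits in one dose column per cycle, in both numerator and denominator.

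The study baseline is also a defensible choice. It is the only drug-free reference, and the SAP uses it throughout for efficacy, laboratory values, residual urine and eGFR. A baseline taken before a later injection follows earlier exposure and can hide cumulative change. Excluding everyone already abnormal at that point would also miss patients who worsen after reinjection. For most chemistry analytes such a rule would leave almost no post-injection values in non-final cycles unless the next pre-injection draw is assigned back. All of this stands, and it argues against replacing the present table.

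PCS tables and adverse-event tables may reasonably answer different questions, occurrence and onset. Abnormal laboratory findings can be reported as adverse events, dose switches are tabulated (SAP 3.2), and the PCS listings show all postbaseline values. Carry-over can therefore be traced patient by patient, but the printed percentages are not corrected. Later-cycle comparisons are not randomised and no test of PCS rates is specified, which limits the consequences without removing the ambiguity. Selective retreatment is possible, but no retreatment criterion in Protocol 5.10.1 concerns a PCS laboratory or vital-sign value.

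**Conclusion.** The recount is real and follows directly from SAP 6.4 and 6.5: new and carried-over abnormalities share one count, labelled with the dose of the cycle in which they are seen. This can inflate later-cycle and higher-dose rates. The size depends on a persistence that the documents do not give. At an assumed 5% new risk it ranges from no inflation to 33.7% in cycle 8, and the upper end needs permanent abnormality and the maximum of eight cycles. At moderate persistence the effect is small in patients: with r = 0.5 and 32 per group without attrition, cycle 2 shows about 2.4 cases instead of 1.6 (32 × 0.074 against 32 × 0.05).

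Weight is the exception. With no observed-value limit, patients aged 12 to 17 followed for 96 to 108 weeks will meet a 5% change increasingly often through growth alone. The primary efficacy analysis is untouched, and the recount does not arise in cycle 1, the only randomised dose comparison.

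**What to change.** Keep the study-baseline PCS tables in SAP 6.4 and 6.5. For cycles 2 onward, add beside them a by-cycle count of new PCS cases:

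- **Cycle baseline:** the last value before that cycle's injection.
- **Numerator:** patients not PCS at cycle baseline with at least one PCS value after that injection.
- **Denominator:** patients not PCS at cycle baseline with at least one later assessment in the cycle.
- **Weight:** judge the 5% change from cycle baseline, with no limit-based exclusion at cycle baseline. For blood pressure and pulse, state which reference the change part uses.
- **Sample assignment:** state that the pre-injection sample of the next treatment belongs to the ending cycle.
- **Worsening:** flag separately patients already PCS at cycle baseline who worsen, in line with SAP 6.2.

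The cost is SAP wording, some programming and one extra table per parameter group. Vital signs, weight, hematology and chemistry are already scheduled before every injection (Protocol Table 1, 6.3.3 and 6.3.14), so no new data are needed. The drawback is small denominators in late cycles. Slow drift across cycles remains visible in the retained tables.

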**Table 5 Vital Sign PCS Criteria**

Parameter	Flag	Criteriaa	
		Observed Value	Change From Baseline
Sitting systolic blood pressure, mm Hg	High	≥ 155	Increase of ≥ 20
	Low	≤ 90	Decrease of ≥ 20
Sitting diastolic blood pressure, mm Hg	High	≥ 105	Increase of ≥ 15
	Low	≤ 45	Decrease of ≥ 15
Sitting pulse rate, bpm	High	≥ 120	Increase of ≥ 15
	Low	≤ 40	Decrease of ≥ 15
Respiratory rate (breaths per minute)	High	> 30	—
	Low	< 12	—
Temperature (°C)	High	> 38	—
	Low	< 36	—
Weight, kg	High	—	Increase of ≥ 5%
	Low	—	Decrease of ≥ 5%

a A postbaseline value is considered potentially clinically significant if it meets both the observed-value and the change-from-baseline criteria.

bpm = beats per minute.

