6.3.4 Vital Signs

Vital signs will be measured at each study clinic visit prior to any invasive procedures as outlined below. The same procedure used for a patient should be used throughout the study.

Pulse rate (beats per minute): Patients should be resting for at least 3 minutes. Pulse rate is then counted over 30 seconds and multiplied by 2.

Blood pressure (mm Hg): The correct size blood pressure cuff for the size of the patient should be used. Patients should be resting for at least 3 minutes. Systolic/diastolic blood pressure is then measured with a sphygmomanometer.

Respiration rate (breaths per minute): Patients should be resting for at least 3 minutes. Respiration rate is counted over 30 seconds and multiplied by 2.

Temperature (°F or °C): Patients should be rested and the body temperature taken according to local site practice (oral, axillary, or tympanic).

Vital signs will be compared to age-appropriate normative values.

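### The two-criterion rule for vital-sign flags in SAP Table 5 cannot be met for respiratory rate, temperature or weight; the relaxed reading makes weight gain track growth; and the age-appropriate comparison in protocol 6.3.4 is not carried through

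*SAP*

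**What the plan says.** Protocol 6.3.4, after describing how pulse, blood pressure, respiration rate and temperature are measured, adds: "Vital signs will be compared to age-appropriate normative values". It names no reference source.

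SAP 6.5 plans descriptive summaries of those four vital signs and then a PCS table by cycle and dose group. Its decision rule is: "Vital sign values will be considered potentially clinically significant (PCS) if they meet both the observed-value criteria and the change-from-baseline criteria". The Table 5 footnote repeats it: "A postbaseline value is considered potentially clinically significant if it meets both the observed-value and the change-from-baseline criteria". Neither text says what to do where a cell holds a dash.

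Table 5 covers six parameters, each with a high and a low row, and has no age or sex bands. The weight row, which has no observed-value limit, reads "Increase of ≥ 5" per cent for the high flag and mirrors this for the low flag. Percentages are based on patients whose study baseline is not PCS. Study baseline is set before treatment 1 and is not reset at later cycles.

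SAP section 13 states that nothing departs from the protocol.

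**The concern.** A rule that joins two conditions with "and" cannot be satisfied when one of them is missing. A programmer must either follow the text, which silences half of the parameters, or decide that a dash means no condition, which the SAP does not say. Two programmers could produce different tables from the same SAP. A zero count for respiratory rate or temperature could mean that nobody crossed the limit or that nobody could have been counted, and the reader could not tell which. Both parameters matter here: urinary tract infection is a study-defined adverse event, and the SAP list of distant-spread terms includes respiratory depression and respiratory failure.

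Weight has a second difficulty. Patients are 12 to 17 years old and stay in the study for 96 to about 108 weeks. A fixed percentage gain from a baseline that never moves will be reached by growth alone if growth is fast enough.

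The limits also show no trace of the age-appropriate comparison that the protocol describes, and the SAP does not acknowledge the difference.

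**Working it through.** **Step 1. Apply the rule to each parameter of Table 5.**

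| Parameter | Observed-value limit | Change limit | Can be flagged if both are required | Can be flagged if a dash means no requirement |
|---|---|---|---|---|
| Systolic pressure | yes | yes | yes | yes |
| Diastolic pressure | yes | yes | yes | yes |
| Pulse | yes | yes | yes | yes |
| Respiratory rate | yes | dash | no | yes, on observed value |
| Temperature | yes | dash | no | yes, on observed value |
| Weight | dash | yes | no | yes, on 5% change |

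Under the stated rule, 3 of 6 parameters cannot be flagged. With a high and a low row each, that is 3 × 2 = 6 of 12 rows.

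**Step 2. Weight under the relaxed reading.** The plan gives no growth rate or expected flag rate, so there is no figure of its own to reproduce. The inputs from the documents are the 5% limit and the 96 to 108 weeks of follow-up (SAP 3.3). The growth rates and body weights below are assumptions.

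- Follow-up in years: 96 × 7 / 365.25 = 1.84; 108 × 7 / 365.25 = 2.07.
- Break-even gain per year = 5% / years: 5 / 1.84 = 2.72% by week 96; 5 / 2.07 = 2.42% by week 108.
- In kilograms by week 96: 0.05 × 40 / 1.84 = 1.09 kg/year at 40 kg; 0.05 × 60 / 1.84 = 1.63 kg/year at 60 kg.
- Change at week 96 = (kg/year × 1.84) / baseline weight. Week at which 5% is reached = (0.05 × baseline weight / kg per year) × 365.25 / 7.

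| Assumed gain | Week-96 change at 40 kg | Week-96 change at 60 kg | Week of +5% at 40 kg | Week of +5% at 60 kg |
|---|---|---|---|---|
| 0.5 kg/year | 2.3% | 1.5% | 209 | 313 |
| 1 kg/year | 4.6% | 3.1% | 104 | 157 |
| 2 kg/year | 9.2% | 6.1% | 52 | 78 |
| 3 kg/year | 13.8% | 9.2% | 35 | 52 |
| 4 kg/year | 18.4% | 12.3% | 26 | 39 |

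At 2 to 4 kg/year the week-96 change is 6 to 18%, and every cell is flagged. At 1 kg/year it is 3 to 5%, just under the limit at 40 kg, and not flagged by week 96.

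**Step 3. Timing.** In the fastest case (4 kg/year at 40 kg), the gain at week 24 is 4 × 24 × 7 / 365.25 = 1.84 kg, or 4.6%. A first cycle of up to 24 weeks would therefore produce no growth flag at these rates. The effect is confined to longer first cycles and to later cycles.

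**Step 4. Age norms.** Protocol 6.3.4 promises an age-appropriate comparison. Table 5 has one limit per row for all patients, and no other SAP section makes an age-based comparison of vital signs. Protocol 6.3.14 makes the same promise for laboratory results; there, Table 4 uses limits of normal supplied by the laboratory and age-banded alkaline phosphatase limits. Table 5 has no counterpart.

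**The case against.** The best answer to the first part is that a dash obviously means no criterion is set, as it does in Table 4, and that nobody would program six dead rows. That is probably what was intended, and it makes this a drafting gap. It does not close the gap. SAP 6.4 flags a laboratory value that meets either limit, so a dash there only removes one route to a flag. Table 5 requires both conditions, so a dash removes a necessary one, and the rule is stated twice without exception.

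The best answer to the second part is that growth rates come from outside the documents and that short first cycles are unaffected. Both points stand, and the conclusion is limited accordingly.

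The best answer to the third is that the protocol sentence sits among the examination procedures, so sites could make the comparison, and that the protocol's safety-analysis section sets no age rule. This also stands in part. It explains how both texts could be true, but the SAP does not say so.

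Some stronger readings are tempting and are not supported:

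- A reader might infer that Table 5 is the only look at vital signs, or that the PCS table cannot show any dose-related signal. SAP 6.5 also plans descriptive summaries by dose and cycle, adverse events are tabulated by dose, and the blood pressure and pulse rows work under either reading.
- A reader might infer that weight is both never flagged and flagged too often. These belong to two different readings of the dash and cannot both hold.
- A reader might infer that the fixed limits are clinically wrong for ages 12 to 17. The documents give no basis for judging that.

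**Conclusion.** The concern holds, at minor severity. The flagging rule cannot be met for respiratory rate, temperature and weight, which is a matter of text and needs no assumption. Relaxing it repairs respiratory rate and temperature, but leaves a weight-increase flag whose break-even of about 2.7% per year by week 96 is low for a growing population. That flags in long or later cycles would largely reflect growth depends on the assumed 2 to 4 kg/year at 40 to 60 kg; at 1 kg/year it would not follow. The mismatch between protocol 6.3.4 and Table 5 is real and undeclared, although it may be one of documentation. What is affected is a descriptive safety table with no hypothesis test. The descriptive vital-sign summaries are unaffected by the dash problem, and the primary efficacy analysis is not touched.

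**What to change.** 1. In SAP 6.5 and the Table 5 footnote, state that where only one criterion is listed for a row, that criterion alone applies. This costs one sentence.
2. Drop the weight-increase flag, or base it on change in an age- and sex-adjusted weight score.
3. Reconcile Table 5 with protocol 6.3.4: name an age-appropriate reference and add that comparison to SAP 6.5, or record the departure in SAP section 13. The reference has to be chosen, because the protocol does not name one.

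The inputs (age, sex, height, weight and vital signs) are already collected. The downside is the modest programming of a reference table for items 2 and 3, which is avoided if the weight-increase flag is dropped and the departure is declared.
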